4.0 Vulnerable Populations

The following special populations will be excluded from this study:

- Adults unable to consent (including adults unable to read and understand English)
- Individuals who are not yet adults (infants, children, teenagers)
- Pregnant women
- Prisoners
- Employees of BostonSight

TITLE: Pilot study to investigate the feasibility, reliability, and efficiency of utilizing ocular surface optical coherence tomography to automate PROSE fitting

PROTOCOL NUMBER: BFS OCT-01

IRB APPROVED

Jul 14, 2020

NCT04649177

5.0 Number of Subjects

A minimum of 10 current PROSE patients with a primary PROSE treatment indication of an irregular ocular surface/irregular cornea (including but not limited to Keratoconus, Pellucid Marginal Degeneration, Ectasia, Post-Penetrating Keratoplasty, Corneal Scar, Trauma) **AND/OR** ocular surface disease will be enrolled in the study. We can approximate a 10-20% drop-out rate, so we will expect to recruit 12 patients total. The first 10 patients to be eligible and complete the study will be used for data analysis.

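### Does recruiting 12 patients fall short of the 10 completers needed at the protocol's own drop-out rate?

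*Protocol*

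**What the plan says.** Protocol section 5.0 (Number of Subjects) makes three statements that bear on the point.

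- Enrolment floor: "A minimum of 10 current PROSE patients with a primary PROSE treatment indication" is to be enrolled, with the qualifying indications listed.
- Assumed loss, and planned recruitment presented as following from it: "We can approximate a 10-20% drop-out rate, so we will expect to recruit 12 patients total".
- Analysis set: "The first 10 patients to be eligible and complete the study will be used for data analysis".

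The section gives no inflation formula. It does not say which point of the drop-out range was used, and it does not say that recruitment stops at 12. Section 6.0 (Recruitment Methods) draws on patients attending the clinic and allows a search of the patient database. Section 26.0 (Resources/Support) expects no difficulty in recruiting.

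**The concern.** The protocol moves from the drop-out range to the figure of 12 as if one followed from the other, and over part of that range it does not. A reader who tests the upper end finds 9.6 expected completers against 10 wanted. One might suspect the common slip of multiplying by 1 + d (10 × 1.2 = 12) where dividing by 1 − d is needed (10/0.8 = 12.5).

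The enrolment floor adds to the doubt. The same number, 10, is both the minimum enrolled and the number of completers to be analysed, and both cannot be met by enrolling exactly 10 when losses are expected. The section also does not say what happens if fewer than 10 complete. If 12 were a hard limit, the study could end below its stated analysis size.

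**Working it through.** **Inputs, all from section 5.0:** completers wanted, 10; drop-out d, 10% to 20%; expected recruitment, 12. The 15% figure is the midpoint of the stated range.

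**Reproducing the 12.** The number to recruit is 10/(1 − d), rounded up.

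| d | 10/(1 − d) | Rounded up | 10 × (1 + d) | Expected completers, 12 × (1 − d) |
|---|---|---|---|---|
| 10% | 11.1 | 12 | 11.0 | 10.8 |
| 15% | 11.8 | 12 | 11.5 | 10.2 |
| 16.7% | 12.0 | 12 | 11.7 | 10.0 |
| 20% | 12.5 | 13 | 12.0 | 9.6 |

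The correct formula returns the protocol's 12 at every drop-out from 10% to 16.7%. The limit is 1 − 10/12 = 16.7%, that is, 2 losses among 12. The mistaken formula also returns 12 at 20%, so the number alone cannot show which route was taken.

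**Size of the gap.** The uncovered part runs from 16.7% to 20%, which is 3.3 of the 10 percentage points, about one third of the range. At its worst the gap is 10 − 9.6 = 0.4 of a patient in expectation, or one recruit after rounding.

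**Chance of at least 10 completers**, assuming independent drop-outs (exact binomial):

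| d | 12 recruited | 13 recruited |
|---|---|---|
| 10% | 0.889 | 0.966 |
| 15% | 0.736 | 0.882 |
| 20% | 0.558 | 0.747 |

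For 12 at 20%: 66 × 0.8¹⁰ × 0.2² + 12 × 0.8¹¹ × 0.2 + 0.8¹² = 0.283 + 0.206 + 0.069 = 0.558. These figures describe a plan that stops at the number shown, which section 5.0 does not say.

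**What one fewer completer costs.** With the same standard deviation, the standard error of a mean from 9 patients is √(10/9) = 1.054 times that from 10, about 5% larger.

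**The case for a change.** The strongest case for a change is that 12 has little slack, and that stands. If recruitment did stop at 12, the chance of reaching 10 completers at 20% drop-out would be 56%.

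Eligibility can erode the number as well. Section 8.0 lists consent before the screening checklist and the confirmation of fit. Inability to hold fixation for imaging (section 3.0) may show only at the scanner, and section 15.0 withdraws those who cannot complete the tasks. Suppose, as an illustration, that 12 counts consented patients and one proves ineligible. Eleven remain, with 9.9 expected completers at 10% drop-out and 8.8 at 20%, and a 70% and 32% chance of reaching 10.

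These figures depend on reading 12 as a ceiling. The text calls it an expectation, sets a floor beneath it, and defines the analysis set by completion. A team one completer short can recruit another patient from the same clinic without departing from the plan.

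The argument from the floor is weaker. Enrolling exactly 10 would give 8 to 9 expected completers and a 35% (at 10% drop-out) or 11% (at 20%) chance of 10. But the next sentence raises the plan to 12 because of drop-out, so those figures describe a study that the protocol does not propose.

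Nor would writing 13 settle the matter. If the standard is expectation, the gap being closed is 0.4 of a patient. If it is a high probability of reaching 10, then 13 gives only 75% at 20% drop-out.

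**Conclusion.** The arithmetic behind the concern is right at one end of the range: at 20% drop-out, 12 recruits give 9.6 expected completers, and 13 would be needed to expect 10. It does not show an error in the protocol, because the correct formula gives 12 from 10% up to 16.7%, including the midpoint. That 12 came from 10 × 1.2 is a guess.

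No change is needed. The gap is one recruit at the top of a range that the protocol itself calls approximate. The missing statement on what to do when fewer than 10 complete is one the study team would fill sensibly, by recruiting one more patient or analysing those who completed. The protocol presents the study as a pilot and rests the number 10 on no power or precision target, so 9 completers would support its conclusions about as well as 10. A sentence saying that recruitment continues until 10 have completed would be tidier, but it would change no result.

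This rests on two readings of section 5.0: that 12 is an expected number and not a cap, and that 10 is a practical target. The probabilities also assume independent drop-outs.

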3.0 Inclusion and Exclusion Criteria

The participant will be eligible to participate if the following criteria apply:

1. Written Informed Consent has been obtained prior to any study-related procedures
2. Male or female, 18 years of age and older prior to the initial visit
3. Established wearer of PROSE in the study eye with an optimized fit in the opinion of the clinician
4. No medical need for a PROSE retreatment or replacement lens at the time of enrollment in the study eye, in the opinion of the clinician
5. Initial PROSE fitting was initiated and completed at BostonSight, Needham
6. Current PROSE device does not have channels or fenestrations

TITLE: Pilot study to investigate the feasibility, reliability, and efficiency of utilizing ocular surface optical coherence tomography to automate PROSE fitting

PROTOCOL NUMBER: BFS OCT-01

IRB APPROVED

Jul 14, 2020

NCT04649177

7. Currently wears a PROSE device in the study eye primarily for an irregular ocular surface /irregular cornea (including but not limited to Keratoconus, Pellucid Marginal Degeneration, Ectasia, Post-Penetrating Keratoplasty, Corneal Scar, Trauma) **AND/OR** ocular surface disease
8. Has the ability to NOT wear the current PROSE device in the study eye for 3 days prior to scan and 3 days prior to first fitting appointment in the opinion of the investigator and subject
9. In the opinion of the investigator, the subject has the ability to follow study instructions
10. In the opinion of the investigator, the subject has the ability to complete all study procedures and visits

The participant would **NOT** be eligible to participate if at least one of the following criteria is met:

1. Is currently participating in any other type of eye-related clinical or research study
2. Is pregnant or nursing as reported by the subject
3. Has a condition or is in a situation which, in the investigator's opinion, may put the subject at significant risk, may confound study outcomes, or may significantly interfere with the subject's participation in the study
4. Has had previous ocular surgery within the past 12 weeks
5. Intolerance to PROSE wear
6. Inability to maintain stable fixation and exposure for ocular surface imaging
7. Corneal touch by the posterior surface of the device in current PROSE device
8. Allergy to sodium fluorescein
9. Patient is an employee of BostonSight
10. Subject is currently incarcerated.

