TITLE: Pilot study to investigate the feasibility, reliability, and efficiency of utilizing ocular surface optical coherence tomography to automate PROSE fitting

PROTOCOL NUMBER: BFS OCT-01

IRB APPROVED

Jul 14, 2020

NCT04649177

Visit 2/3:

Visit Location and Subject Preparation

This visit for the scanning of the ocular surface will take place at EYEdeal, Scanning, LLC ([name]) under the oversight of [name] and under an additional IRB approved protocol and consent (submitted separately by [name]).

The measurements taken with the “EYEdeal Scanning ophthalmic instrument” are performed non-mydriatic (pupil dilation drops will not be administered). Scanning tomography measurements will be performed at the EYEdeal Scanning facility by an EYEdeal engineer, with the assistance of a licensed optometrist or ophthalmologist from BostonSight who will carefully expose the ocular surface by holding the eyelids open in a suitable position for scan acquisition. The EYEdeal Engineer will be in charge of and completely controlling all aspects of the “EYEdeal Scanning Ophthalmic Instrument”. The EYEdeal engineer will have no contact and will not perform any examination or procedure on the patient. The licensed BostonSight optometrist or ophthalmologist will have no interaction and no control of the “EYEdeal Scanning Ophthalmic Instrument”. The licensed BostonSight optometrist will interact with the patient and perform the eyelid maneuvers as described above.

Methodology

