procedures and protections in place at EYEdeal Scanning. Images, video, and data collected on the subjects are maintained on a single computer according to subject identification numbers. The randomly-chosen identification numbers are assigned during the first subject visit and will be stored separately from all other data. The identification numbers can only be linked to the subject via a single password-protected encrypted data file maintained by the PI. Password protected de-identified scan data will be provided to BostonSight on a flash drive or via email.

Data Analysis

The laser scan will produce a series of eye surface height data along each scanned meridian. This data will be processed by an algorithm to determine the shape of the measured meridian. All meridians will then be stitched together to generate a large area topography map and image of the eye. If the data is deemed inadequate or unreliable scans are obtained or optimal scans are not achieved within 1 hour, or if in excess of 10 scans are required, the subject may return on a future date for one additional visit to EYEdeal Scanning, LLC with the same time and scan number constraints.

BostonSight Fitting Visit (no lens for 3 days prior to visit)

Pre-visit calls:

- Contact subject one week before visit to complete COVID-19 travel form
- Contact subject 4 days before visit to remind them not to wear lenses for the next three days.
- Contact subject one day before visit to complete COVID-19 screening form

Visit 4:

- Update medical and ocular history
- Baseline Slit Lamp Biomicroscopy without PROSE device or any contact lens applied in the study eye
- Image-guided PROSE* fit evaluation
 - Slit Lamp Biomicroscopy evaluation of image-guided PROSE device fit in study eye.
 - BCVA (over-refraction as needed) – prescription will be based on current optimized standard PROSE lens
- PROSE device performance questionnaire (after 45 minutes of wear, if able/tolerable)
 - Awareness
 - Comfort
- Post 45 minutes wear time evaluation:

TITLE: Pilot study to investigate the feasibility, reliability, and efficiency of utilizing ocular surface optical coherence tomography to automate PROSE fitting

PROTOCOL NUMBER: BFS OCT-01

IRB APPROVED

Jul 14, 2020

NCT04649177

- Slit Lamp Biomicroscopy evaluation of image-guided PROSE device fit
- Optical Coherence Tomography imaging of central corneal clearance
- iTRACE imaging of lens rotation and decentration

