9.0 Study Endpoints

The primary endpoints in this study are as follows:

1. Fit evaluation of image-guided PROSE device
 - a) Overall fit parameters (slit lamp)
 - b) Central clearance ordered vs central clearance observed (slit lamp and OCT)
 - c) iTRACE (rotation and decentration)
2. Evaluate ability to dispense after manufacturing one PROSE device with image guided system (YES/NO)
3. PROSE device performance questionnaire (awareness and comfort both graded 0 to 10)

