15.0 Withdrawal of Subjects

Subjects will be withdrawn from the study if they are unable to complete the tasks in the study protocol. In addition, if they experience an adverse event in which the investigator does not feel that the subjects should continue, they will be withdrawn.

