23.0 Data Management

Data will be stored in a study paper file at BostonSight. Electronic data will be stored on a password-protected computer in a locked office. All study data will remain at BostonSight for a minimum of 3 years following study completion. The principal investigator will be responsible for maintaining study data security and subject confidentiality, and the PI and the study coordinator will be responsible for receipt and transmission of the data. The investigative team and inspectors from regulatory agencies such as the US Food and Drug Administration will have access to the data if requested for study monitoring or an audit.

All collected data will be documented on study documents and analyzed for differences between baseline and test data. Hypothesis testing will be performed using statistical analyses including parametric or nonparametric comparisons (i.e., t-tests, signed-rank tests), analysis of variance, general linear models, correlation, or regression techniques.

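### Analysis is limited to the first ten completers, so on the natural reading an eye that never yields an adequate scan leaves the analysis and no endpoint shows it

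*Protocol*

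**What the plan says.** Section 1.0 of the protocol names feasibility first among its three aims. Section 5.0 sets a minimum of 10 subjects, expects 10-20% drop-out, plans to recruit 12, and then states: "The first 10 patients to be eligible and complete the study will be used for data analysis".

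Section 8.0 (Visit 2/3) anticipates scanning problems: "If the data is deemed inadequate or unreliable scans are obtained or optimal scans are not achieved within 1 hour", or if more than 10 scans would be needed, "the subject may return on a future date for one additional visit to EYEdeal Scanning, LLC". The same limits apply to that visit. No outcome is given if it also fails.

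Section 15.0 adds: "Subjects will be withdrawn from the study if they are unable to complete the tasks in the study protocol".

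Section 9.0 lists three primary endpoints and no others: the fit of the image-guided device, the dispensing judgement ("Evaluate ability to dispense after manufacturing one PROSE device with image guided system (YES/NO"), and the awareness and comfort questionnaire. Section 10.0 makes the scan data the input for manufacturing the device.

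**The concern.** Obtaining a usable scan is the first step of the method under test. If eyes that fail this step are removed before analysis, the analysed set shows no scan failures by construction. The dispensing rate then answers a narrower question: among eyes that could be scanned and given a device, how many could be dispensed? That is a valid rate, but it is not the feasibility of image-guided fitting in eligible wearers. The listed endpoints do not let a reader tell how far apart the two are.

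The words *first 10* have a second effect. With 12 recruited, an 11th or 12th completer would be left out even with full data.

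**Working it through.** **1. The plan's own figure.** Recruits needed for 10 completers at drop-out d are 10/(1 - d):

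- d = 10%: 10/0.90 = 11.1, rounded up to 12
- d = 15%: 10/0.85 = 11.8, rounded up to 12
- d = 20%: 10/0.80 = 12.5, rounded up to 13

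The stated 12 is reproduced over most of the range, and the recruitment figure is not at issue. Recruiting 12 and analysing 10 leaves up to 2/12 = 16.7% outside the analysis.

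**2. Where a scan failure goes.** With no adequate scan there is no input for the device (section 10.0), so there is nothing to evaluate at Visit 4. Endpoints 1 and 2 cannot be scored, and endpoint 3 has a baseline value but no test value. Section 15.0 then points to withdrawal, and section 5.0 removes the subject from analysis. An eye that reaches Visit 4 and fits poorly is not affected, because it is scored NO.

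**3. Relative size.** Let f be the share of drop-out that is scan failure. Remove unrelated drop-outs from both denominators and assume all completers are analysed. Then

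completer rate / rate with scan failures as NO = (1 - d(1 - f))/(1 - d)

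| f | d = 10% | d = 20% |
|---|---|---|
| 0 | 0.900/0.90 = 1.00 | 0.80/0.80 = 1.00 |
| 25% | 0.925/0.90 = 1.03 | 0.85/0.80 = 1.06 |
| 50% | 0.950/0.90 = 1.06 | 0.90/0.80 = 1.13 |
| 100% | 1.000/0.90 = 1.11 | 1.00/0.80 = 1.25 |

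**4. Absolute size if exactly ten of 12 complete.** The two drop-outs include 0, 1 or 2 scan failures. Intervals are exact (Clopper-Pearson) 95%. The numbers dispensable are assumed.

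| Dispensable | 0 failures (/10) | 1 failure (/11) | 2 failures (/12) | Gap in points for 1; 2 failures |
|---|---|---|---|---|
| 6 | 60% (26-88) | 55% (23-83) | 50% (21-79) | 5.5; 10.0 |
| 8 | 80% (44-97) | 73% (39-94) | 67% (35-90) | 7.3; 13.3 |
| 10 | 100% (69-100) | 91% (59-99.8) | 83% (52-98) | 9.1; 16.7 |

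The scan-success proportion would separate these cases: 10/12 = 83% (52-98%) if both drop-outs were scan failures, 12/12 = 100% (74-100%) if neither was.

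**5. If more than ten complete.** The direction is no longer fixed:

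- All 12 complete, the first ten give 8 YES and the last two are YES: 8/10 = 80% against 10/12 = 83%.
- All 12 complete and the last two are NO: 8/10 = 80% against 8/12 = 67%.
- Eleven complete and one eye is a scan failure, with 4 YES in the first ten and YES for the eleventh: 4/10 = 40% against 5/12 = 42%.

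This case is not remote. With 12 recruits and independent drop-out, the chance of at least ten completers is 0.889 at 10% drop-out and 0.558 at 20%. The chance of exactly ten is 66 × 0.9^10 × 0.1^2 = 0.230 and 66 × 0.8^10 × 0.2^2 = 0.283. So eleven or twelve complete with probability 0.889 - 0.230 = 0.659 and 0.558 - 0.283 = 0.275.

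**The case against.** **Exclusion already covers it.** Section 3.0 excludes "Inability to maintain stable fixation and exposure for ocular surface imaging". The reasons for repeat scans given in section 8.0 (motion, exposure, blinks, saccades) largely match this, and a clinician can judge fixation and lid exposure at the Visit 1 slit lamp. This stands in part: residual scan failure may be small, and f near 100% is the least supported end of the range. But Visit 1 lists no trial scan, and section 8.0 still foresees inadequate data after enrolment.

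**Non-completion is inferred.** No sentence says that an eye failing both scanning visits is withdrawn, completing the study is not defined, and a subject who sat for the scans arguably did the task. This stands. It is why confidence is moderate, and it is itself a reason to define the term.

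**The data are kept elsewhere.** Scanning runs "under an additional IRB approved protocol and consent", which is not at hand and may report adequacy. Section 23.0 also says: "All collected data will be documented on study documents and analyzed for differences between baseline and test data". Scan success may therefore be recorded, and nothing forbids reporting it. But this protocol does not bring it into its endpoints, and an eye without a device has no test fit to compare with baseline.

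**It is a small pilot.** There is no success threshold and the intervals overlap widely. That is true. The point is what the rate describes, not whether a difference is significant.

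**Tempting stronger readings.** A reader might infer that the protocol expressly discards scan failures, or that the dispensing rate must be too high. The text supports neither: the first is an inference, and the second holds only when exactly ten complete and at least one drop-out is a scan failure. Nor does the text say that designs or devices rejected at the check in section 13.0 leave the analysis. It does not say whether they are remade, scored NO or withdrawn.

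**Conclusion.** The point holds in a limited form and should be fixed. The protocol itself fixes a completer-only set and endpoints that all require a device, so this is not a detail left to an analysis plan. On the natural reading, an eye with no adequate scan falls outside both, which leaves part of the first-named objective unmeasured here.

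The 0 to 17 point gap rests on three assumptions: 12 are recruited, exactly ten complete, and 0 to 2 of the drop-outs are scan failures. The protocol gives no scan-failure rate, so the true effect may be zero. With eleven or twelve completers the reported rate may be too high or too low. Confidence is moderate because the status of a twice-failed scan is inferred.

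**What to change.** Replace the last sentence of section 5.0 with text to this effect:

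> All eligible subjects with at least one attempted scan are analysed, and every completer is used. The proportion of eyes with an adequate scan is reported (first visit; either visit), with all scanned eyes as the denominator. Endpoint 2 is reported (a) among scanned eyes, counting as NO an eye that has no adequate scan after its last attended scanning visit, including a subject who does not return after an inadequate first scan; and (b) among eyes evaluated with a device. Subjects with an adequate scan who leave for reasons unrelated to scan or device are removed from the denominator of (a) and listed with the reason. Any design or device rejected before wear is listed with its reason. A subject is not reclassified as ineligible under exclusion 6 after a scan has been attempted.

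Define *adequate scan* and *complete the study*, and state in advance how a design or device rejected before wear is scored in (a).

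The cost is a written adequacy criterion, a per-visit adequacy record from the scanning site (which works under its own protocol and must agree to supply it), and a rate that may look less favourable. No visits or subjects are added.

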7.0 Multi-Site Research Communication – N/A

8.0 Study Timelines

It is anticipated that to enroll all study subjects, it will take approximately 3 months. The estimated date for completion of this study is 6 months after the start of recruitment.

The total duration of the subjects' participation in the study will be approximately 1-2 months (to complete all 3-4 visits). The visits include:

- Initial screening visit/baseline evaluation at BostonSight
- Scanning visit at EYEdeal Scanning, LLC (Needham, MA)
- One additional follow up scanning visit at EYEdeal Scanning, LLC (as necessary)
- Lens fitting evaluation visit

Study Visits:

TITLE: Pilot study to investigate the feasibility, reliability, and efficiency of utilizing ocular surface optical coherence tomography to automate PROSE fitting

PROTOCOL NUMBER: BFS OCT-01

IRB APPROVED

Jul 14, 2020

NCT04649177

Initial Visit at BostonSight (present wearing PROSE device for at least 45 minutes)

Pre-visit calls:

- COVID-19 screening and travel forms:
 - Contact subject one week before visit to complete COVID-19 travel form
 - Contact subject one day before visit to complete COVID-19 screening form

Visit 1:

- Complete Informed Consent
- Complete patient screening checklist
- Complete medical and ocular history intake
- Document information about current PROSE device in the study eye
 - Current PROSE device parameters
 - Number of cuts needed to dispense initial standard PROSE lens in study eye (chart review)
- Current PROSE device performance questionnaire (0-10 scale)
 - Awareness
 - Comfort
- Check current VA with PROSE (logMAR, Appendix D)
- PROSE fit evaluation
 - Slit Lamp Biomicroscopy evaluation of current PROSE device fit in study eye
 - Confirm acceptable fit, no further customizations, replacement or retreatment required at this time (inclusion criteria requirement)
- Baseline Slit Lamp Biomicroscopy without PROSE device or any contact lens applied in the study eye

EYEdal Scanning, LLC Visit(s) (Needham, MA) (within 4 weeks of Initial BostonSight Visit, no lens for 3 days prior to visit):

Pre-visit calls:

- Contact subject one week before visit to complete COVID-19 travel form
- Contact subject 4 days before visit to remind them not to wear lenses for the next three days.
- Contact subject one day before visit to complete COVID-19 screening form

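### Section 5.0 recruits 12 but analyses only the first 10 completers, so an 11th or 12th subject with complete data is discarded for no stated reason

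*Protocol*

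**What the plan says.** Protocol Section 5.0 makes three statements about numbers. Enrolment is to be "A minimum of 10 current PROSE patients". Recruitment allows for losses: "We can approximate a 10-20% drop-out rate, so we will expect to recruit 12 patients total". The analysis set is then fixed: "The first 10 patients to be eligible and complete the study will be used for data analysis". Nothing is said about the data of an 11th or 12th completer.

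Section 23.0 (Data Management) says, without exception, that the data collected will all be recorded and analysed for baseline-to-test differences.

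Section 8.0 allows a second scanning session. If scans are inadequate or unreliable, or the time or scan limit is reached, "the subject may return on a future date for one additional visit to EYEdeal Scanning, LLC". A subject therefore has three or four visits over about one to two months. On accrual, Section 8.0 says: "It is anticipated that to enroll all study subjects, it will take approximately 3 months".

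The primary endpoints in Section 9.0 (fit, ability to dispense after one device, and the performance questionnaire) rest on the Visit 4 assessments.

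**The concern.** Recruiting a margin for drop-out is sound. Throwing away the margin when drop-out turns out low is not needed to achieve that aim. The excluded subjects would have gone without their device before scanning and again before fitting, and a study lens would have been made for each. In a study of 10 to 12 subjects, two discarded completers are up to 2/12, or one sixth, of the completed data. Read literally, Sections 5.0 and 23.0 cannot both be followed once an 11th subject completes.

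The way the ten are chosen also matters. The sentence reads most naturally as order of reaching completion. That order depends partly on how readily the eye could be scanned, which is part of what the study is evaluating. An analysis set should not depend on the performance of the technology under test.

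**Working it through.** **1. The plan's own figure.** Number to recruit so that 10 are expected to complete, 10/(1 - d), with d from Section 5.0:

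- d = 10%: 10/0.90 = 11.1, rounded up to 12
- d = 15%: 10/0.85 = 11.8, rounded up to 12
- d = 20%: 10/0.80 = 12.5, rounded up to 13

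The stated 12 is reproduced at 10% and 15%, and is one short at 20%. The number 12 is not the problem; the analysis rule is.

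**2. When a completer is discarded.** With 12 recruited, two drop-outs leave exactly 10 completers and nobody is discarded. The rule bites only when 11 or 12 complete, that is, with fewer than two drop-outs.

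**3. How likely that is.** Assume 12 eligible recruits and independent drop-out, with completion probability q = 1 - d. Then P(11 or 12 complete) = 12(1 - q)q^11 + q^12.

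| Drop-out | P(11 complete) | P(12 complete) | P(at least one discarded) | Expected number discarded |
|---|---|---|---|---|
| 10% | 0.377 | 0.282 | 0.659 | 0.377 + 2 × 0.282 = 0.94 |
| 15% | 0.301 | 0.142 | 0.443 | 0.301 + 2 × 0.142 = 0.59 |
| 20% | 0.206 | 0.069 | 0.275 | 0.206 + 2 × 0.069 = 0.34 |

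**4. What the lost data are worth.** For the YES/NO dispensing endpoint, the exact (Clopper-Pearson) 95% lower limit when all are YES is 0.025^(1/n). This is 0.69 for n = 10 and 0.74 for n = 12. As an illustration of how far the estimate could move, suppose 8 of the first 10 are YES and both later completers are NO. The rule reports 8/10 = 80% (95% CI 44-97%), where all completers give 8/12 = 67% (35-90%). That pattern is a chosen extreme.

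**5. Order of completion.** For the same entry date, an added scanning session on a later date tends to delay the lens and Visit 4. The protocol does not give the repeat rate or the delay, so any size is an assumption. An illustrative simulation took entry uniform over 13 weeks, a base duration of 4-8 weeks and drop-out unrelated to repeat scanning. With a 25% repeat rate and a 2-week delay, a completer is discarded with these probabilities:

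- 10% drop-out: 0.149 if a repeat scan was needed, 0.066 if not
- 20% drop-out: 0.063 if a repeat scan was needed, 0.027 if not

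Over repeat rates of 10-50% and delays of 1-4 weeks, the ratio of these two probabilities runs from about 1.5 to about 7. With no delay it is 1. The result shows the direction if there is a delay; it does not estimate the effect in this trial.

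**The case against.** In favour of the rule it can be said that a fixed analysis number is a simple stopping convention for an uncontrolled pilot, that fewer than one completer is expected to be lost, and that a lower limit of 69% rather than 74% changes little. The loss is indeed small in absolute terms. But keeping the data costs nothing, and the protocol gives no reason for dropping them.

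Three stronger readings are tempting and do not stand.

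- **That the rule biases the results in the device's favour.** A reader might infer that hard-to-scan eyes finish last, are dropped, and would have fitted worse. Section 8.0 places the scanning visits within 4 weeks of the initial visit and gives one duration range for three or four visits, so a repeat-scan subject need not finish later than a single-scan one. The longest assumed delays in the simulation run past the stated 1-2 months. Entry dates spread over about 3 months also drive the order. In the 25% repeat, 2-week case only 43-44% of discarded completers are repeat-scan eyes, so most are not. Nor does anything link a second session to worse fit: the repeat visit exists to obtain adequate scans, exclusion 6 in Section 3.0 removes eyes that cannot hold fixation and exposure, and Section 13.0 has a clinician check each design and device.
- **That a minimum of 10 contradicts a cap of 10.** The minimum governs enrolment and the cap governs analysis. The two are compatible.
- **That order of completion is certainly meant.** If order of enrolment among completers is meant, the scanner-related selection largely disappears. The discarding, and the conflict with Section 23.0, remain.

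**Conclusion.** The point holds as a defect in the analysis-set rule. At the protocol's own drop-out range, there is a 27% to 66% chance that one or two subjects with complete data are excluded without a reason, against Section 23.0. These figures assume that exactly 12 eligible subjects are recruited and that drop-out is independent between subjects.

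Dependence of the selection on the scanner is plausible under the natural reading of the sentence and is worth removing. Its size, and any resulting distortion of fit, clearance or dispensing results, cannot be derived from the protocol and should not be asserted. The sentence should be changed because the gain is free, not because a bias has been shown.

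**What to change.** Replace the last sentence of Section 5.0 with: *All enrolled eligible subjects who complete Visit 4 will be included in the data analysis; at least 10 completers are planned.* This agrees with Section 23.0 and removes any dependence on finishing order among completers. List the results by whether a repeat scanning visit was needed, so that a reader can see whether those eyes differ.

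Do not add a hard stop at 12 enrolled. Section 5.0 only expects 12. With exactly 12 enrolled, the chance of fewer than 10 completers is 11%, 26% and 44% at 10%, 15% and 20% drop-out, so room to replace drop-outs should stay.

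The cost is one sentence and one extra column in a listing. No additional patients, visits or lenses are required, because the subjects concerned are already recruited and followed. Subjects withdrawn under Section 15.0 before Visit 4 stay outside this analysis set; the change does not address them.
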